Page 14 of 53 IDEAL BACKPACS Protocol Final Version 1.1 date 09-Oct-l2024

Table 1: Referral strategy performance

	Sensitivity	Specificity	Likelihood ratio
Braun 2-step	0.90	0.60	1.82
Modified Braun 2-	0.86	0.73	2.10
step			
CaFaSpA >1	0.94	0.31	1.25
CaFaSpA > 2	0.61	0.74	1.98
ASAS >1	1.00	0.16	1.82
Baraliakos	0.91	0.67	2.78

Only the modified Braun [45] strategy and the subsequent Baraliakos strategy [9] achieve a likelihood ratio >2. The modified Braun strategy [45] was suggested for use in the NICE spondyloarthritis clinical guideline [3], but this guideline predates the Baraliakos strategy [9] which has a higher likelihood ratio and is itself a simplification of the Braun strategy.

The Baraliakos strategy clearly has the potential to improve the supporting evidence base for incorporating an axSpA referral strategy into clinical practice. However, there are some aspects of this study that suggest that it needs independent validation and that it may not perform identically in the population it is intended to screen.

Firstly, the study recruited from both GP practices (30%) and community orthopaedic clinics (70%), so may reflect a slightly different healthcare system and population than might be encountered in a pure primary care setting. The study recruited from community clinics surrounding a single tertiary centre and was not multicentre, potentially limiting the evidence base for referral strategy roll out. Participants were 45 years of age or younger, so it does not provide an evidence base for individuals over 45. The ASAS classification criteria include patients having onset of back pain before 45 years (who with delayed diagnosis might well be over 45 years at the time of referral). There

are also some concerns that the Baraliakos paper modelled a large number of potential referral strategies, with no adjustment for multiple comparisons which might result in an overestimate of the benefits of the strategy [47]. The optimal Baraliakos strategy includes raised CRP, response to NSAIDs and HLA-B27 testing, which necessitate clinical follow up to assess whether individuals are positive for these variables. This additional potential burden on primary care clinicians may have a detrimental impact on the feasibility, acceptability, and consequent uptake of the Baraliakos referral strategy.

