Therefore, although the Baraliakos strategy does appear to outperform Braun [45], it still requires validation in an independent prospective multicentre primary care cohort and an assessment of implementation feasibility in primary care. The data required to be collected to validate this strategy also provides an exciting opportunity to iteratively model a new alternative referral strategy, against which the existing Baraliakos strategy can be compared. This new strategy would have the potential to address many of the concerns mentioned above.

However, should the Baraliakos model prove superior, the development of an electronic pop up on GPs IT systems to inform referral from primary care, would help lower barriers to its use.

Page 15 of 53 IDEAL BACKPACS Protocol Final Version 1.1 date 09-Oct-l2024

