3.1.3 Index tests

Index tests are the BACKPACS model (to be developed within this study) in addition to existing referral strategies described in Table 3.

Page 17 of 53 IDEAL BACKPACS Protocol Final Version 1.1 date 09-Oct-l2024

Table 3: Index tests

Index tests	Assessment
The Baraliakos strategy [9]	Assesses 3 clinical variables. If 2 or 3 of these variables are present (or a 'second step' HLA-B27 test is positive) then secondary care referral is suggested:
	 improvement in pain with NSAIDs after 48 hours raised CRP (blood test)
	• early morning stiffness (≥ 30minutes)
	This strategy requires follow up after the initial primary care clinic appointment.
The Modified Braun strategy [45]	Assesses 10 clinical variables and if at least 4 of these 10 variables are present then secondary care referral is suggested:
	 low back pain that started before the age of 35 years waking during the second half of the night because of symptoms buttock pain
	 improvement with movement improvement with non-steroidal anti-inflammatory drugs (NSAIDs)
	 a first-degree relative with spondyloarthritis, current/past arthritis,
	• current/past enthesitis
	current/past psoriasisHLA-B27 genetic test
The 'Assessment of SpondyloArthritis international Society (ASAS) strategy [44]	Patients with chronic backpain (≥ 3 months) with onset before 45 years, should be referred if at least one clinical variable is present:
1	Inflammatory backpain HLA-B27 positive
	 Sacroiliitis on imaging, if available (x-ray or MRI) Peripheral manifestations (arthritis, enthesitis and/or dactylitis)
	 Extra-articular manifestations (psoriasis, inflammatory bowel disease and/or uveitis) Family history for spondyloarthritis
	Good response to NSAIDS Acute elevated phase reactants (c-reactive protein or erythrocyte sedimentation rate)
The CaFaSpA referral strategy[15]	Easy to use and was developed in a primary care setting but was not adopted by NICE spondyloarthritis clinical guideline[3], as the study cohort reported a much lower than expected prevalence of HLA-B27 positive individuals. The explanation for this may be related to the study having a lengthy retrospective recruitment time

Page 18 of 53 IDEAL BACKPACS Protocol Final Version 1.1 date 09-Oct-l2024

for individuals with CBP (median 10 years), whilst
excluding patients diagnosed with axSpA during this
period; many of the excluded individuals with axSpA
would have been HLA-B27 positive. This approach

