4.1.4 Secondary care assessment

All participants will be seen in specialist rheumatology research clinics. If the participant does not attend their scheduled appointment they will be contacted by email, text and/or telephone to reschedule. If the participant is still unresponsive after up to 3 attempts to contact then the GP will be informed of their withdrawal from the study.

Page 28 of 53 IDEAL BACKPACS Protocol Final Version 1.1 date 09-Oct-2024

The secondary care assessment will consist of:

- Clinical assessment
- Blood sample collection
- X-ray
- Research MRI scan (likely to be a separate appointment)

On arrival at the local secondary care research clinic, if participants have not completed the study questionnaire electronically, they will be asked to do so as part of their consultation. There may be an option to complete a paper version of the questionnaire.

At the clinic appointment, an appropriately trained member of the clinical team will perform the semi-structured clinical research assessment (30 minutes for clinical assessment and 30-60 minutes for bloods and x-ray), evaluating axSpA features, using a standardised proforma listed in Table 6.

Participants will be asked if they have had a spinal/SIJ MRI scan in the last 12 months, if this is the case then the participant's previous MRI result will be assessed alongside the results of the research MRI scan.

Table 6: axSpA features evaluated in secondary care clinical assessment

axSpA feature	Method of assessment	Definition
Clinical assessmen	nt	
Peripheral arthritis	66/68 peripheral joint assessment	66/68-Swollen and Tender Joint Counts (SJC66/TJC68) Joints assessed include temporomandibular joint, (0-2) Sternoclavicular joint (0-2), Acromioclavicular joints (0-2), Glenohumeral(s) (0-2), Elbow(s) (0-2), Wrist(s) (0-2), Metacarpal phalangeal joints (0-10), Finger Proximal interphalangeal joint (0-10), hip(s) (tender score only 0-2), knee(s) (0-2), ankle(s) (0-2), metatarsal phalangeal joints (0-10), toe PIP(s) (0-10) The joint count is scored as a sum of the swollen joints (0-66) and the sum of the tender joints (0-68)
	Dactylitis count	Past or present dactylitis diagnosed by a physician (categorised as present/absent) with current dactylitis count 0-20 ref
	Heel enthesitis	Presence of Achilles Tendonitis and/or Plantar Fasciitis
	Enthesitis	Spondyloarthritis Research Consortium of Canada (SPARCC) Enthesitis Index

Page 29 of 53

IDEAL BACKPACS Protocol Final Version 1.1 date 09-Oct-2024

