		and Leeds Enthesitis Index (LEI)
		16 sites assessed in total: the greater trochanter, quadriceps tendon insertion into the patella, patellar ligament insertion into the patella and tibial tuberosity, Achilles tendon insertion, plantar fascia insertion, medial and lateral epicondyles, and the supraspinatus insertion. Presence or absence of tenderness; max
		score = 16
Mobility	Bath Ankylosing Spondylitis Metrology Index (BASMI)	Index comprising 5 measures of spinal and hip mobility
Personal history	 a. Onset of chronic back pain symptoms b. Dactylitis c. Enthesitis d. Skin/nail psoriasis, e. Colitis f. Uveitis g. Anterior chest pain 	Self-reported, current and previous
Family history	Presence in first degree or second- degree relatives* of any of the following: a. Skin/nail psoriasis b. Colitis c. Uveitis, d. axSpA, e. Reactive arthritis, f. PsA	Self-reported (yes/no) and number of relatives affected
Response to NSAIDs	Only if NSAID response is not completely clear. At least one week at max tolerated dose. (If NSAID response if not completely clear) for individuals with no contraindications, min 7-day course of full dose NSAIDs (with telephone evaluation of NSAID response from research team at 1 week)	Self-reported (yes/no)

Page 30 of 53 IDEAL BACKPACS Protocol Final Version 1.1 date 09-Oct-2024

Blood tests	Blood tests			
Diagnostic laboratory tests	HLA-B27	Positive testing according to standard laboratory techniques.		
	CRP	C-reactive protein above upper normal limit in the presence of back pain, after exclusion of other causes for elevated CRP concentration.		
Imaging				
x-ray	Conventional SIJ plain x-rays	Modified New York criteria for each SIJ		
MRI	SIJ and whole spine (30 min scan) arranged within 4 weeks** of clinical assessment.	 (i) Description of oedema and structural features (fat metaplasia, erosions, ankylosis) in SIJs – yes/no for each. Interpretation according to ASAS specifications (bone marrow oedema in typical location 'highly suggestive' of axSpA) - yes/no for MRI positivity (ii) Are there unequivocal features of spinal inflammation? (yes/no) (iii) Overall impression across x-ray and MRI – (a) normal (b) equivocal (c) axSpA (d) other 		

^{*}First degree relative includes an individual's parents, siblings and children. Second degree relative includes grandparent, grandchild, half siblings, aunt/uncle and niece/nephew. **where possible, waiting times may vary between sites.

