4.6 Collection, Storage and Analysis of Clinical Blood Samples (HLA-B27 / CRP)

The blood samples will be tested for the presence of HLA-B27 and CRP level. Collection, storage and analysis of clinical blood samples will be in line with local secondary care laboratories standard operating procedures. Samples for NHS pathology analysis will be labelled in accordance with local NHS procedures. Samples will not be retained at the end of the study and will be destroyed in accordance with the Human Tissue Act, 2004.

It is the responsibility of the study site to ensure that samples are appropriately labelled in accordance with the study procedures to comply with the 2018 Data Protection Act. Biological samples collected from participants as part of this study will be transported, stored, accessed and processed in accordance with national legislation relating to the use and storage of human tissue for research purposes and such activities shall at least meet the requirements as set out in the 2004 Human Tissue Act and the 2006 Human Tissue (Scotland) Act.

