86. Braun V, Clarke V: Using thematic analysis in psychology. Qualitative Research in Psychology

2006, 3(2):77-101.

- 87. Braun VC, V.: Thematic analysis. Research methods in social sciences: An A-Z of key concepts: Open University Press.; 2021.
- 88. Creswell JW, Miller DL: Determining Validity in Qualitative Inquiry. Theory Into Practice 2000, 39(3):124-130.

Appendices

Appendix 1: Specification of the variables used for the ASAS-Criteria for classification of Axial Spondylarthritis

Clinical Feature of axSpA	Definition
Inflammatory back pain (IBP)	IBP according to experts: 4 out of 5 of the
, , , , , , , , , , , , , , , , , , ,	following parameters present:
	1. Age at onset < 40 years
	2. Insidious onset
	3. Improvement with exercise
	4. No improvement with rest
	5. Pain at night (with improvement upon getting up)
Good response to NSAIDs	24-48 hours after a full dose of a non-steroidal
	anti-inflammatory drug (NSAID) the back pain is
	not present any more or much better.
	(the clinical co-applicants on the PGfAR IDEAL
	grant have concluded that response after one
	week would be more appropriate)
Arthritis	Past or present active synovitis diagnosed by a physician.
Dactylitis	Past or present dactylitis diagnosed by a
	physician.
Enthesitis	Heel enthesitis: past or present spontaneous
	pain or tenderness at examination of the site of
	the insertion of the Achilles tendon or plantar
	fascia at the calcaneus.
	(a broader evaluation of enthesitis is also being
	evaluated for the IDEAL study cohort)
Psoriasis	Past or present psoriasis diagnosed by a
	clinician.
Inflammatory bowel disease (IBD)	Past or present Crohn's disease or ulcerative
	colitis diagnosed by a physician.
Uveitis anterior	Past or present uveitis anterior, confirmed by an
	ophthalmologist.
Family history	Presence in first-degree or second-degree
	relatives of any of the following:
	a. Ankylosing spondylitis
	b. Psoriasis
	c. Uveitis
	d. Reactive arthritis
	e. IBD
HLA-B27	Positive testing according to standard laboratory
	techniques.
Elevated CRP	C-reactive protein above upper normal limit in
	the presence of back pain, after exclusion of
	other causes for elevated CRP concentration.

Page 53 of 53 IDEAL BACKPACS Protocol Final Version 1.1 date 09-Oct-2024

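### The protocol defines a positive CRP in two ways and does not say which one scores the Baraliakos and ASAS referral strategies

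*Protocol*

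**What the plan says.** - **Index test.** Table 3 (Section 3.1.3) gives the Baraliakos CRP item as "raised CRP (blood test"), with no condition on cause. The rule reads: "If 2 or 3 of these variables are present (or a 'second step' HLA-B27 test is positive) then secondary care referral is suggested". In the same table the ASAS referral strategy lists raised acute phase reactants, also unconditionally, and one positive item is enough for referral. The modified Braun list has no CRP item.
- **Data collection.** Table 6 (Section 4.1.4) defines CRP as "C-reactive protein above upper normal limit in the presence of back pain, after exclusion of other causes for elevated CRP concentration".
- **Origin of that wording.** Appendix 1 has the same definition ("C-reactive protein above upper normal limit in" and so on) among the variables for the ASAS classification. Section 3.1.2 makes that classification the secondary reference standard.
- **Who completes Table 6.** In the rheumatology research clinic, "an appropriately trained member of the clinical team will perform the semi-structured clinical research assessment".
- **What the laboratory does.** Section 4.6 says: "The blood samples will be tested for the presence of HLA-B27 and CRP level". Samples are then destroyed (Sections 4.2.1 and 4.6).
- **Intended use.** Section 1.2 foresees "the development of an electronic pop up on GPs IT systems to inform referral from primary care". It also says that CRP, NSAID response and HLA-B27 are items "which necessitate clinical follow up to assess whether individuals are positive for these variables".

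**The concern.** CRP is one of only three step-one items in the rule that the first co-primary objective validates. As an existing Baraliakos predictor it may also be a BACKPACS candidate. The Table 3 item is a laboratory result. The Table 6 item is a laboratory result plus a decision that nothing else explains it.

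Under Table 6, a participant without axSpA whose CRP is above the limit can be recorded as negative because another cause was found. The decision falls to the secondary-care team. The local PI or delegate at the same site later makes the reference diagnosis (Section 4.1.6). Masking is stated in one direction only: the reviewing rheumatologist does not see screening-tool results. Nothing separates the CRP attribution from the clinical picture.

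At stake are the specificity and likelihood ratio reported for the rule, and the comparison between strategies, because the definition touches Baraliakos and ASAS but not modified Braun as listed. Specificity also enters the cost equation in Section 6.

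**Working it through.** **1. The plan's own figure.** Section 5.2 assumes 14% prevalence, sensitivity 90% and specificity 65%, and claims over 90% power with 720 patients against lower bounds of 79% and 58%. Cases: 720 × 0.14 ≈ 101; non-cases: 619. Alpha and sidedness are not stated. Exact one-sample binomial tests give:

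| One-sided alpha | Power, sensitivity 90% vs 79% | Power, specificity 65% vs 58% |
|---|---|---|
| 0.05 | 0.922 | 0.972 |
| 0.025 | 0.792 | 0.943 |

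The claim reproduces at one-sided 0.05. The CRP question does not alter this calculation; it decides which rule the 65% describes.

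**2. Direction.** The Table 6 condition can only turn CRP positives into negatives. With the other items fixed, it can only turn a positive rule result into a negative one. So specificity stays equal or rises, and sensitivity stays equal or falls.

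**3. Formula for non-cases.** Let q = NSAID response, s = morning stiffness, c = CRP above the limit, b = HLA-B27 positive, e = share of raised CRPs attributed to another cause. Assume the items are independent within non-cases.

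- P(at least 2 of 3) = qs + [q(1−s) + s(1−q)]c
- Specificity = (1−b)[1 − P(at least 2 of 3)]
- Gap (Table 6 minus plain) = (1−b)[q(1−s) + s(1−q)]ce

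**4. One worked case (all inputs assumed).** q = s = 0.40, b = 0.08, c = 0.20, e = 0.50.

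- Plain: 0.16 + 0.48 × 0.20 = 0.256; specificity 0.92 × 0.744 = 68.4%
- Table 6: 0.16 + 0.48 × 0.10 = 0.208; specificity 0.92 × 0.792 = 72.9%
- Gap: 4.4 points before rounding. LR+ at sensitivity 90%: 0.90/0.316 = 2.85 against 0.90/0.271 = 3.32. This overstates the LR+ gain, because sensitivity is held fixed although Table 6 can lower it.

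**5. Range (all inputs assumed).**

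| Set | c | e | q and s | b | Smallest gap | Largest gap |
|---|---|---|---|---|---|---|
| A | 10–30% | 10–50% | 30–50% | 6–9% | 0.91 × 0.42 × 0.10 × 0.10 = 0.4 points | 0.94 × 0.50 × 0.30 × 0.50 = 7.1 points |
| B | 15–25% | 25–75% | 30–45% | 8% | 0.92 × 0.42 × 0.15 × 0.25 = 1.4 points | 0.92 × 0.495 × 0.25 × 0.75 = 8.5 points |

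**6. What a gap would mean.** Suppose 65% were obtained under Table 6 and the plain rule were lower. Non-cases = 619, one-sided alpha 0.05, sensitivity held at 90%:

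| Gap (points) | Plain specificity | LR+ | Power against 58% | Extra false positives |
|---|---|---|---|---|
| 0 | 65% | 2.57 | 0.97 | 0 |
| 1 | 64% | 2.50 | 0.92 | 6 |
| 3 | 62% | 2.37 | 0.64 | 19 |
| 5 | 60% | 2.25 | 0.25 | 31 |
| 7 | 58% | 2.14 | 0.05 | 43 |

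LR+ stays above the benchmark of 2 that Section 1.2 cites in every row, since 0.90/(1 − specificity) ≥ 2 needs specificity of only 55%.

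**The case against.** The strongest reply is that Table 3 defines the index tests and Table 6 only describes the clinic assessment. On that reading the item is already the plain one. CRP level is measured, results go to the local PI and reports are entered in the database (Section 4.1.6), so a value-based item may be derivable. Deriving index-test variables is ordinary work for the SAP, which is not shown.

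Much of this stands. A reader might infer several stronger points that the documents do not support:

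- **That specificity is inflated.** No section says the index item is scored from Table 6.
- **That a specialist makes the exclusion.** The text names a trained member of the clinical team for the assessment. It does not say who rules out other causes, or when.
- **That a GP could not make the judgement.** Section 1.2 expects clinical follow-up for CRP in primary care. One can say only that no step for ruling out other causes is described there.
- **That the study departs from the published rule.** The source study's operational definition is known here only through the short entry in Table 3.

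The eligibility criteria also remove some other causes of a raised CRP (known inflammatory arthritis, suspected cancer, bone or disc infection), which limits the gap.

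The reply does not settle the matter, because Table 6 governs what sites record. The protocol does not require the number and the laboratory limit to be stored. If only the adjudicated result is kept, no SAP can recover the plain item without going back to site laboratory records.

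**Conclusion.** Tables 3 and 6 define CRP differently, and the protocol does not say which definition scores the index tests. The direction is certain only on condition that Table 6 is used: specificity equal or higher, sensitivity equal or lower, than for the rule as listed in Table 3. The size cannot be derived from the documents, which give no item prevalences in non-cases and no share of raised CRPs attributed elsewhere. With assumed values and independent items, the specificity gap runs from about 0.4 to 8.5 points. Only the upper end is comparable with the planned 7-point margin; the worked case gives 4.4 points. This is an ambiguity in a co-primary index item that should be closed before the data are locked. It is not a demonstrated bias.

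**What to change.** - In Table 6 and the eCRF, record the numeric CRP, its units and the laboratory's upper limit.
- State that the CRP item of the Baraliakos and ASAS referral strategies, and any BACKPACS CRP candidate, is scored from the value alone (above that laboratory's limit).
- Keep the version that requires other causes to be ruled out as a separate field, used for the ASAS classification as secondary reference standard.
- Report index accuracy under the adjudicated version as a sensitivity analysis, giving sensitivity as well as specificity.

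The cost is one extra CRF field and a short edit to Table 6. The reported specificity may be slightly less favourable.

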4.1.5 Research MRI appointment

An appointment will be made for participants to attend a separate radiography appointment for a research MRI (it may be possible for the research MRI to be on the same day as the clinical assessment, bloods and x-ray). Appointment dates will be entered to the study database by the research team. Where possible, appointment reminders will be sent to participants (by the research team or the coordinating centre) including a request for the participant to notify the study team of any changes since their previous appointment e.g. if the participant has fallen pregnant within that time.

Participants will be asked to stop taking NSAIDs for one week before the MRI scan, they will be asked to take other medication, such as paracetamol instead, if necessary. NSAIDs can reduce bone marrow oedema on MRI so make it more difficult to detect signs of axSpA. Stopping NSAIDs may increase the diagnostic sensitivity. NSAID cessation for 1 or 2 weeks is now routine practice in the NHS prior to MRIs for suspected axSpA.

The participant will attend the research MRI scan and the SIJ and whole spine scanned. MRI techniques will follow the ASAS specifications [64] (see 3.1.2 Reference standard Appendix 1: Specification of the variables used for the ASAS-Criteria for classification of Axial

Page 31 of 53
IDEAL BACKPACS Protocol Final Version 1.1 date 09-Oct-2024

Spondylarthritis) for identification of inflammatory bone marrow oedema and structural changes (erosions, sclerosis or ankylosis). See 4.2 Study Procedures for further information.

If the participant does not attend the initial scheduled MRI appointment, then they will be contacted to reschedule the appointment. If they continue to be unresponsive after up to 3 attempts to contact, no further attempts will be made and they will be withdrawn from the study.

Radiographs and MRIs will be read locally for safety, to exclude urgent conditions such as unexpected malignancy. Any unexpected results (including red flags) will be communicated urgently to the GP via letter (and an additional telephone call if clinically indicated) from the local PI (or delegate) so they can proceed with participant's care as appropriate.

X-rays and MRIs will also be centrally reviewed by at least two experienced musculoskeletal radiologists blinded to participants' clinical and laboratory data. The imaging reports will be uploaded to the study database.

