4.2.2 Imaging

Radiographs

For participants aged 18 and over, conventional SIJ plain x-rays will be taken.

Page 32 of 53

IDEAL BACKPACS Protocol Final Version 1.1 date 09-Oct-2024

MRI

MRI scans will be acquired according to a dedicated imaging protocol. Participants will have an MRI scan of their SIJ and whole spine (30 min scan) arranged within 4 weeks (where possible) of clinical assessment. For some secondary care sites, the MRI scan may be on the same day as the clinical assessment, if there is capacity. MRI scans will be acquired according to a dedicated imaging protocol which will be provided separately.

Briefly, SIJ MRI acquisitions will be performed in modified coronal plane (aligned with the long axis of the SIJ), using small field-of-view imaging and consistent resolution (matrix size) between the acquisitions.

We will acquire:

- T2-weighted STIR or turbo STIR imaging
- T1-weighted turbo spin echo imaging a
- T2-weighted Dixon turbo spin echo imaging (repeated with two effective echo times).

For the spine imaging, we will cover the whole spine in the sagittal plane, using either two or three blocks, using (i) T2-weighted STIR or 'turbo' STIR imaging and (ii) T1-weighted turbo spin echo imaging.

Data upload

Image data will be acquired in DICOM format and pseudo-anonymised by individual sites, before being uploaded to the XNAT platform for image storage and curation. Each site will have their own folder on the XNAT platform to minimise the risk of data leaks between sites.

Scan interpretation

All scans will be read by two consultant radiologists on the XNAT platform. If discrepancies exist regarding the overall impression of whether axSpA is present (i.e. whether the patient is 'imaging positive') across the MRI and x-ray, a third consultant radiologist will perform an additional read and make a final decision on the appropriate category.

The following will be included in the x-ray report:

Modified New York criteria grade 0-4 for each SIJ.

The following will be included in the MRI report:

- Description of oedema and structural features (fat metaplasia, erosions, ankylosis) in SIJs – yes/no for each.
- Interpretation according to ASAS specifications (bone marrow oedema in typical location 'highly suggestive' of axSpA) - yes/no for MRI positivity
- Are there unequivocal features of spinal inflammation? yes/no

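### The protocol does not sequence the study-directed NSAID course and the NSAID stop before MRI; with a clinic-day start the two overlap for scans on days 1–13

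*Protocol*

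**What the plan says.** Four statements in the protocol bear on this.

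- **The course.** The row on response to NSAIDs in Table 6 (section 4.1.4) applies "Only if NSAID response is not completely clear". For those participants, if there is no contraindication, it directs a "min 7-day course of full dose NSAIDs (with telephone evaluation of NSAID response from research team at 1 week". No start day is given.
- **The stop.** Section 4.1.5 says "Participants will be asked to stop taking NSAIDs for one week before the MRI scan" and gives the reason: "NSAIDs can reduce bone marrow oedema on MRI so make it more difficult to detect signs of axSpA". It makes no exception for participants on the course.
- **The scan date.** Table 6 and section 4.2.2 place the MRI within 4 weeks of clinic where possible. Section 4.2.2 adds that "the MRI scan may be on the same day as the clinical assessment, if there is capacity", and 4.1.5 says the same. No minimum interval between clinic and scan is set for participants on the course.
- **The schedule.** Table 4 shows neither the course nor the stop.

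Both results are used later. Under section 3.1.2 the primary reference standard is a rheumatologist's diagnosis on all clinical and diagnostic parameters, with scores 7–8 counted as axSpA and 1–6 (normal or equivocal) as not. In Table 3, NSAID response is an item in the Baraliakos, modified Braun and ASAS strategies.

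**The concern.** One instruction puts a participant on NSAIDs for at least a week after clinic. The other takes the same participant off NSAIDs for the week before a scan that may fall at any point in the following 4 weeks. For some permitted dates a site cannot follow both, and the protocol does not tell it what to do.

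Two measurements are at risk. A scan taken during or soon after the course may miss bone marrow oedema and could move a true case from 7–8 to 1–6, which the primary analysis counts as not axSpA. If the stop is kept instead, the one-week NSAID response that Table 6 asks for is missing or rests on a shortened course. The participants concerned are selected by an unclear answer on an item of the index tests, so any resulting error need not be random with respect to those tests.

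**Working it through.** The protocol states no figure for this, so there is none to reproduce. The check is calendar arithmetic.

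**Inputs**

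- Course length L = 7 days, the stated minimum (Table 6).
- Stop length W = 7 days before the scan (4.1.5).
- Scan day D = 0 to 28, with clinic as day 0 (Table 6, 4.1.5, 4.2.2).
- Course start day s: **not in the protocol**. I take s = 0, the natural reading of an item in the clinic proforma with a call at one week, and also try s = 1 and a course deferred until the scan day or later.

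**Overlap condition.** The course occupies days s to s + L − 1. The stop occupies days D − W to D − 1. They share at least one day when

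s + 1 ≤ D ≤ s + L + W − 1.

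**Results**

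| Course | Scan days in conflict | Scan days free of conflict |
|---|---|---|
| s = 0, L = 7 | 1 to 0 + 7 + 7 − 1 = 13 | 0 and 14–28 |
| s = 1, L = 7 | 2 to 1 + 7 + 7 − 1 = 14 | 0–1 and 15–28 |
| s = 0, L = 2 (48-hour response only) | 1 to 0 + 2 + 7 − 1 = 8 | 0 and 9–28 |
| Started on the scan day or later | none | all |

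With s = 0, 13 of the 28 days after clinic are in conflict (13/28 = 46%). The earliest scan after a completed course and a full stop is on day 7 + 7 = 14. Day 0 is free only if the first dose follows the scan. Each day beyond the 7-day minimum moves the upper limit one day later.

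**What gives way, for s = 0**

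- *Course kept in full.* A scan on days 1–6 falls within the course. On day 7 or later the number of NSAID-free days before the scan is D − 7: none on day 7, 6 on day 13, and the required 7 only on day 14.
- *Stop kept in full.* For a scan on days 1–7 the stop reaches back to day 0 or earlier, so no dose can be taken before the scan. For a scan on days 8–13 the course is cut to D − 7 days: 1 day for day 8, 6 days for day 13.

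**The case against.** The strongest reply is that this is an unstated order and not a contradiction. A site can meet both instructions by booking the scan on days 14–28, inside the window, or by running the course after the scan. The window is qualified by a where-possible clause and participation may last up to 6 months (section 3.4.3), so there is time. This is correct. A reader might infer that the index item or the scan must be compromised for any MRI on days 1–13; the documents do not support that. Only participants with an unclear response and no contraindication take the course, and the start day is not given. What remains is that nothing in the protocol leads a site to a compliant route.

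A reader might also infer that a shortened course spoils the Baraliakos item. Table 3 defines that item as "improvement in pain with NSAIDs after 48 hours", so a course stopped after 48 hours can still supply it. What is lost is the one-week response in Table 6, which Appendix 1 records as the timing the co-applicants thought more appropriate. Even if only 48 hours were needed, a clinic-day start conflicts with scans on days 1–8.

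Nor is the MRI the whole reference standard. X-ray, structural MRI changes, HLA-B27 and any MRI from the previous 12 months also inform the diagnosis, and so does NSAID response itself. There is therefore no clean division into a damaged index test or a damaged reference standard, and the documents give no basis for how many diagnoses would change. A count of affected participants or cases would need the share taking the course and the spread of scan dates, and neither is given.

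Finally, the case report form and the separate imaging protocol are not shown, so NSAID dates may be recorded somewhere. It can only be said that the protocol's own list of items does not include NSAID intake at the scan.

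**Conclusion.** The point holds as a sequencing gap. Two stated instructions collide on dates the protocol permits, and no section orders them. With a clinic-day start the collision covers scans on days 1–13 (days 2–14 with a next-day start) in participants who take the course. It disappears for later scans in the window or for a course run after the scan.

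The day count rests on the assumed start day and on the 7-day minimum. It describes the calendar and is not a proportion of participants, which cannot be derived from the documents. Bias in the accuracy estimates is possible, not shown. The gap still deserves correction: the protocol itself names the mechanism by which NSAIDs can hide the MRI finding, a missed finding would count against axSpA in the primary analysis, and from the items the protocol lists the affected scans could not reliably be picked out afterwards.

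**What to change.** - Reconcile the NSAID row of Table 6 with sections 4.1.5 and 4.2.2, and show the agreed sequence in Table 4. The order of course, stop and scan, and any clinical rule, are for the clinical team.
- Record the date of the last NSAID dose at the MRI visit, if the case report form does not already do so.
- Add a sensitivity analysis of the accuracy estimates that excludes participants scanned less than one week after their last NSAID dose. The detail can sit in the SAP, but the analysis depends on that date being collected.

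The cost is a scheduling statement, one data field and one extra analysis. Some scans or NSAID calls may move, which the where-possible wording and the 6-month participation period can absorb. The date field should be in place early, because the information is hard to recover once scans have been done without it.
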